13.2 QC Plan

A second review statistician will independently reproduce the primary analyses and summary statistics in table 2. All analytic output will include the date and time, source dataset, and author.

13.3 Code for Primary and Secondary Analyses

Analyses will be conducted in SAS v 9.4 (SAS Institute, Cary NC).

PROC GENMOD DATA=data;

CLASS trt site klg enroll;

MODEL koosp_chg = trt site KLG enroll koosp_bl;

CONTRAST 'Group 1 vs Group 4' trt -1 0 0 1;

CONTRAST 'Group 2 vs Group 4' trt 0 -1 0 1;

CONTRAST 'Group 1 vs Group 2' trt -1 1 0 0;

LSMEANS trt / PDIFF DIFF CL ALPHA=0.0167;

run;

14 Shell Tables

Table 1: Participant Features at Baseline

| | Total cohort | Arm 1 Home Exercise | Arm 2 Home Ex + Adherence | Arm 3 Home Ex + Adherence + PT (placebo) | Arm 4 Home Ex+ Adherence + PT (strengthening) |
|----------------------------|-----------------|---------------------------|---------------------------------|---|---|
| Number of subjects | | | | | |
| Site [N, (%)] | | | | | |
| Brigham and Women's | | | | | |
| University at Buffalo | | | | | |
| University of Pittsburgh | | | | | |
| Cleveland Clinic | | | | | |
| Sex [N, (%)] | | | | | |
| Male | | | | | |
| Female | | | | | |
| Race | | | | | |
| White | | | | | |
| Black, African American | | | | | |
| Asian | | | | | |
| Native American, Pacific | | | | | |
| Islander | | | | | |
| Multiple races endorsed | | | | | |
| Not answered | | | | | |
| Ethnicity | | | | | |
| Hispanic | | | | | |
| Not Hispanic | | | | | |
| Educational attainment | | | | | |
| High school or less | | | | | |
| Associate degree or some | | | | | |
| college | | | | | |
| College degree and higher | | | ******* | | |
| K-L Grade[N, (%)] | | | | | |
| 0 | | | | | |
| 1 | | | | | |
| 2 | | | | | |
| 3 | | | | | |
| Age (mean (SD)) | | | *** | | |
| Body Mass Index (mean (SD) | | | **** | | |
| Enrollment date [N, (%)] | | | | | |
| Prior to March 15, 2020 | | | | | |
| After March 15, 2020 | | - | | | |

Table 2: Primary and secondary outcomes

| | Arm 1 Home Exercise | Arm 2 Home Ex + Adherence | Arm 3 Home Ex + Adherence + PT (placebo) | Arm 4 Home Ex+ Adherence + PT (strengthening) | Arm 4 vs. Arm 1 | Arm 4 vs. Arm 2 | Arm 2 vs Arm 1 |
|---|--|-------------------------------------|--|---|--------------------|--------------------|--------------------|
| KOOS Pain Baseline 3 months 3 mo – BL | Mean (SD) Mean (SD) Mean (SD) | Mean (SD) Mean (SD) Mean (SD) | Mean (SD) Mean (SD) Mean (SD) | Mean (SD) Mean (SD) Mean (SD) | Mean (98.3% CI) | Mean (98.3% CI) | Mean (98.3% CI) |
| KOOS ADL Baseline 3 months 3 mo - BL | | | | | | | |
| EQ-5D Baseline 3 months 3 mo - BL | | | | | | | |
| Quadriceps Strength Baseline 3 months 3 mo – BL | | | | | | | |
| Hamstring Strength Baseline 3 months 3 mo – BL | The state of the s | | | | | | |
| Gluteus Medius Strength Baseline 3 months 3 mo – BL | | | | | | | |
| 40 meter timed walk Baseline 3 months 3 mo – BL | | | | | | | |
| 30 second sit to stand Baseline 3 months 3 mo – BL | Mahara | | | | | | |
| Single leg stand Baseline 3 months 3 mo – BL | | | | | | | |

Table 3: Adverse Events

| | Total cohort | Arm 1 Home Exercise | Arm 2 Home Ex + Adherence | Arm 3 Home Ex + Adherence + PT (placebo) | Arm 4 Home Ex+ Adherence + PT (strengthening) |
|--|-----------------|---------------------------|---------------------------------|---|---|
| Serious adverse events Deaths Hospitalizations (overnight admission) APM TKR Total | | | | (Indiana) | , (a.e., g., |
| Adverse events APM (index knee) Other MSK Cardiovascular Neurological Pulmonary Infectious Other Total | | | | | |

Figure 1: CONSORT Diagarm

Figure 2: A figure showing the longitudinal results of KOOS Pain, KOOS ADL at baseline, 3, 6, 12 months (mean value for each group with 95% confidence intervals.

Additional tables to be presented in appendix:

- Analysis of secondary hypotheses for primary and secondary outcomes (arm 3 vs. arm 2, arm 3 vs arm 4).
- Descriptive statistics (n, mean, standard deviation, 95% confidence interval) of longitudinal outcomes (baseline, 3m, 6m, 12m) KOOS pain, KOOS ADL.
- Treatment durability overall and by treatment group
- Sensitivity analysis for missing data: Primary and secondary outcomes

15 Bibliography

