8.5 Sample Size

We power the trial to detect a modest effect of 0.33 SD, reasoning that patients and clinicians will adopt treatments with modest effects if the intensity of treatment and risk of harm is low. As the KOOS Pain scale had a baseline SD of 16 points in MeTeOR, an effect size of 0.33 SD equates to 5.3 points, less than the estimated minimally clinically important difference for the KOOS Pain scale of 8-10 points^{9,13}. We envision that the difference between Arm 1 (least intensive) and Arm 4 (most intensive) will be 10-12 points and that the comparisons of Arms 1 vs. 2 (effect of adherence optimization), 2 vs. 3 (additional provider interaction), and 3 vs. 4 (additional therapist-directed exercise and manual therapy) will represent components of this overall difference. Thus, our plan to power for a difference of 5.3 points in pairwise comparisons should provide adequate power for all contrasts. We assume 80% power and Type I error of 0.0167 to reflect three comparisons of strategies that would be used in practice (Arms 4 vs. 1; Arms 4 vs. 2; Arms 2 vs. 1). Given these considerations and balanced allocation across arms, each Arm would need 194 subjects. Allowing for 10% dropout at one year we will require 194 x 1.1 = 214 subjects per Arm, 856 in total.

9 Analytic Considerations

9.1 Hypotheses

This study will address the following hypotheses, summarized in Table 2:

| Table 2. Study Hypotheses | | | | | | | | | | | |
|---------------------------|-----------------------|--|-----------------------|------------------------------------|--|--|--|--|--|--|--|
| Arm | Arm 1 (home exercise) | Arm 2 (home exercise w/adherence optimization) | Arm 3 (placebo PT) | Arm 4 (therapist- delivered PT) | | | | | | | |
| Arm 1 | | | | | | | | | | | |
| Arm 2 | H3 | | | | | | | | | | |
| Arm 3 | | H4 | | | | | | | | | |
| Arm 4 | H1 | H2 | H5 | | | | | | | | |

Primary Hypotheses:

Hypothesis 1: Arm 4 (protocolized home program, adherence optimization, in-clinic physical therapist-delivered exercise and manual therapy) is more efficacious than Arm 1 (protocolized home program alone). This analysis contrasts the putatively most potent intervention against the least potent.

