11.1 Primary Analysis

In the primary analysis we will test the 3 hypotheses outlined in section 7.1. As placebo is not used in practice, we do not consider tests involving Arm 3 as one of our multiple comparisons. For the primary analysis the alpha level is adjusted to 0.0167 to account for 3 comparisons. We will adjust for randomization arm, the randomization stratification factors of study site and baseline KL grade (0-2 vs. 3) as well as baseline KOOS pain and enrollment date (prior to or after March 15, 2020).

We will use linear regression as our main analytic approach, as our primary outcome of change in KOOS pain is continuous. The primary analysis will be complete case. Data will be summarized by treatment group with the number, mean, and standard deviation. 98.3% Cis will be used to summarize the three between-group comparisons of interest.

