11.6 Multiple testing

In the primary analysis we will test the 3 hypotheses outlined in section 7.1. As placebo is not used in practice, we do not consider tests involving Arm 3 as one of our multiple comparisons. For the primary analysis the alpha level is adjusted to 0.0167 to account for 3 comparisons. Secondary hypotheses and outcomes will not be adjusted for multiple testing.

12 Analysis of Safety Endpoints

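### The PROC GENMOD code for the primary analysis gives intervals about 0.8% too narrow and tests each hypothesis at about 0.0176 rather than 0.0167; familywise error stays below 5%

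*SAP*

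**What the plan says.** Section 11.1 names the method: "We will use linear regression as our main analytic approach, as our primary outcome of change in KOOS pain is continuous". The analysis is complete case and adjusts for arm, site, KL grade, baseline KOOS Pain and enrollment period. On intervals the same section says: "98.3% Cis will be used to summarize the three between-group comparisons of interest". Section 11.6 repeats the level: "For the primary analysis the alpha level is adjusted to 0.0167 to account for 3 comparisons".

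Section 13.3 gives the code. It opens with "PROC GENMOD DATA=data", and the model line is "MODEL koosp_chg = trt site KLG enroll koosp_bl". Three CONTRAST statements follow, one per primary hypothesis, and then "LSMEANS trt / PDIFF DIFF CL ALPHA=0.0167". No distribution, scale or degrees-of-freedom option appears. Shell Table 2 asks for a mean difference with a 98.3% interval for each of the three comparisons.

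The SAP does not discuss the variance estimator or the reference distribution, and it does not say whether the CONTRAST or the LSMEANS p-value decides a hypothesis.

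**The concern.** Ordinary linear regression estimates the residual variance as RSS/(N−p) and takes its limits from the t distribution. For a normal response PROC GENMOD, left at its defaults, differs in three ways:

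- The variance is the maximum-likelihood estimate RSS/N, which is smaller.
- The LSMEANS limits and p-values use normal quantiles, which are smaller than t quantiles.
- CONTRAST reports a likelihood-ratio chi-square test and no estimate.

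The first two both narrow the interval, so under normal errors the departure is always anti-conservative. The third means that each hypothesis gets two p-values, a likelihood-ratio one from CONTRAST and a Wald one from LSMEANS. The differences and intervals for Table 2 can come only from LSMEANS. Section 13.2 also has a second statistician reproduce the primary analyses. If that person follows the text of section 11.1 with a least-squares procedure, the estimates will match but the standard errors, limits and p-values will not.

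What is at stake is whether the stated per-comparison level and coverage are what the code delivers, and whether one unambiguous test decides each primary hypothesis.

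**Working it through.** **Inputs**
- Alpha 0.0167 per comparison (sections 11.1 and 11.6).
- 856 randomized, 214 per arm, SD 16 (section 8.5).
- About 5% dropout at 3 months (section 11.5): 856 × 0.95 = 813 complete cases.
- Mean parameters: intercept 1 + arm 3 + site 3 (four sites in shell Table 1) + KL grade 1 + enrollment period 1 + baseline 1 = 10. If KL grade entered with all four levels there would be 12.
- Assumed: SAS defaults as described, and normal errors with equal variance.

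**The plan's own figure.** Section 8.5 says "We power the trial to detect a modest effect of 0.33 SD" with 80% power and arrives at 194 per arm. A two-sided t-test at 0.0167 (noncentral t) gives power 0.7985 with 193 per arm and 0.8009 with 194. The figure is reproduced and the level is two-sided; a one-sided 0.0167 would need only about 162.

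**Interval width** (N = 813, p = 10, N−p = 803)
- Normal quantile: z = 2.3932. t quantile on 803 df: 2.3983.
- Ratio of the maximum-likelihood to the usual standard error: √(803/813) = 0.9938.
- Width ratio: 2.3932 × 0.9938 / 2.3983 = 0.992, so the interval is 0.8% too narrow.
- In points at SD 16, with N/4 = 203.25 per arm: standard error 16 × √(2/203.25) = 1.587. The t-based half-width is 2.3983 × 1.587 = 3.81. The GENMOD half-width is 2.3932 × 0.9938 × 1.587 = 3.78.

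Section 8.5 gives 16 as a baseline SD, so the point values are illustrative. The ratio does not depend on the SD.

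**Actual size of each test**, in terms of the least-squares t statistic
- Wald (LSMEANS): rejects when |t| > 2.3932 × 0.9938 = 2.378. Size = 2·P(T₈₀₃ > 2.378) = 0.0176; coverage 98.24%.
- Likelihood ratio (CONTRAST): rejects when N·ln(1 + t²/803) > 2.3932², that is |t| > √(803 × (exp(5.7276/813) − 1)) = 2.383. Size = 0.0174.
- t-based regression: rejects when |t| > 2.398. Size = 0.0167; coverage 98.33%.

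Using normal quantiles alone would give 0.0169, so most of the excess comes from the variance estimator.

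**Where results could differ.** For |t| between 2.378 and 2.383 the two GENMOD tests disagree with each other. For |t| between 2.383 and 2.398 both reject where linear regression would not.

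**Range**

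| N | p | Wald | Likelihood ratio |
|---|---|---|---|
| 856 | 10 | 0.0176 | 0.0174 |
| 813 | 10 | 0.0176 | 0.0174 |
| 813 | 12 | 0.0178 | 0.0176 |
| 776 (194 × 4) | 12 | 0.0178 | 0.0176 |

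**Familywise error.** The three contrasts are the pairwise differences among Arms 1, 2 and 4, so they are correlated. Simulation with 4 million replicates at N = 813 and p = 10 gives 0.044 with t-based regression, 0.046 with the GENMOD Wald tests and 0.046 with the likelihood-ratio tests.

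**The case against.** The strongest reply is that this does not matter. The half-width changes by 0.03 points against a target difference of 5.3, the size of each test by 0.0009, and the estimates not at all. Some of the coverage gap is within the SAP's own rounding, since a 98.3% label corresponds to alpha 0.017 while the code uses 0.0167. All of this stands, and it makes the point minor.

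A second reply is that there is no contradiction. Section 11.1 does not specify least squares or t limits, and a normal model fitted by maximum likelihood is linear regression with the same coefficients. Section 11.2.2.1 also foresees generalized linear models for some secondary outcomes, so one procedure throughout is a plausible choice. This largely stands: the procedure is not a different model. But the intervals and tests still miss the level that the SAP states, and the SAP leaves two p-values per hypothesis.

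A third reply is that the benchmark is itself approximate, because KOOS Pain is a bounded score and so neither procedure is exact. That is fair, and the figures should be read under the normal equal-variance assumption.

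In the other direction, a reader might multiply 3 × 0.0176 = 0.053 and infer that overall type I error control is lost. That product is only an upper bound. The contrasts share arms, and the actual familywise error is about 4.6%. A reader might also expect a larger distortion from heavier missing data, but the primary outcome is a self-administered questionnaire and section 11.5 anticipates only about 5% dropout at 3 months.

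**Conclusion.** The point holds as a small departure of the code from the stated level. Each primary test runs at 0.0176 (Wald) or 0.0174 (likelihood ratio) instead of 0.0167, coverage is 98.24%, and the intervals are 0.8% too narrow. Familywise error rises from about 4.4% to 4.6% and remains below 5%, so the documents do not support any claim that multiplicity control fails. Only a result very near the threshold could change, and there the unnamed choice between two p-values matters as well.

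The conclusion rests on SAS default behavior that the SAP does not state, on 813 complete cases derived from planned enrollment and anticipated dropout, on 10 mean parameters, and on normal errors with equal variance. The correction is worth making because it is free, not because the trial's conclusions are at risk.

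**What to change.** In section 13.3, replace PROC GENMOD with a least-squares or REML procedure that keeps the same CLASS and MODEL terms. Either of these will do:

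- PROC GLM with CLPARM and ALPHA=0.0167 as options on the MODEL statement, plus three ESTIMATE statements. In PROC GLM the limits for ESTIMATE are set on the MODEL statement, so adding ALPHA= to ESTIMATE would not work.
- PROC MIXED with three ESTIMATE statements, each with the options CL ALPHA=0.0167.

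The coefficients on trt are −1 0 0 1 for Arm 4 vs Arm 1, 0 −1 0 1 for Arm 4 vs Arm 2, and −1 1 0 0 for Arm 2 vs Arm 1. These match the direction of the column headings in Table 2. State that the estimate, interval and p-value reported for each primary hypothesis all come from these t-based results.

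The cost is a few lines of SAP code. It needs no new data, changes no estimate and has no practical downside.

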11.2 Secondary Analyses

11.2.1 Secondary Hypotheses

In a similar fashion to the primary analysis, we will test the two secondary hypotheses outlined in section 7.2 for the outcome of 3 month KOOS pain.

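### For H4 and H5 on KOOS Pain, the section 13.3 code prints 98.33% limits, although the text reserves these for the three primary comparisons and leaves secondary hypotheses unadjusted

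*SAP*

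**What the plan says.** Section 11.6 sets the multiplicity rule: "For the primary analysis the alpha level is adjusted to 0.0167 to account for 3 comparisons". It places the placebo arm outside that family ("As placebo is not used in practice, we do not consider tests involving Arm 3 as one of our multiple comparisons") and adds: "Secondary hypotheses and outcomes will not be adjusted for multiple testing". Section 11.1 is consistent with this on intervals: "98.3% Cis will be used to summarize the three between-group comparisons of interest". Those three are H1 (Arm 4 vs 1), H2 (4 vs 2) and H3 (2 vs 1).

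For H4 (3 vs 2) and H5 (4 vs 3), section 11.2.1 says only "In a similar fashion to the primary analysis, we will test the two secondary hypotheses outlined in section 7.2", for KOOS Pain at 3 months. It names no alpha and no confidence level.

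The code section is headed "13.3 Code for Primary and Secondary Analyses" and holds one program. Its model is "MODEL koosp_chg = trt site KLG enroll koosp_bl". Its three CONTRAST statements are H1, H2 and H3. Its last statement is "LSMEANS trt / PDIFF DIFF CL ALPHA=0.0167".

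In section 14, shell Table 2 has columns for the three primary contrasts only. The 98.3% label appears in its KOOS Pain row, and the contrast cells in the other rows are blank. H4 and H5 go to an appendix table for which no confidence level is given.

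**The concern.** H4 and H5 have no CONTRAST statement, so the LSMEANS line is the only place in the program that produces these two differences. It produces them with limits at the level adjusted for three comparisons. An analyst who runs the program as written, under a heading that covers secondary analyses, would report 98.33% intervals for two hypotheses that the text places outside the adjustment.

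H5 is the SAP's only contrast of active with placebo therapy, and section 6.1 identifies the lack of evidence against placebo as a key research gap. Readers will judge that contrast largely by its interval. If p lies between 0.0167 and 0.05, the reported interval would include zero while the unadjusted p-value fell below 0.05, and the SAP does not say which to follow. The QC in section 13.2 covers the primary analyses and the summary statistics in Table 2. H4 and H5 are reported in the appendix, so that check need not catch the mismatch.

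**Working it through.** **Inputs.** From section 8.5: SD 16, effect 0.33 SD (5.3 points), 80% power, alpha 0.0167, 194 per arm needed and 214 per arm recruited. From section 11.5: about 5% dropout at 3 months. The evaluable number at 3 months is therefore between 194 (the planned analysis size) and 214 × 0.95 = 203. The unadjusted level is taken as two-sided 0.05. That is an inference from 0.05/3 = 0.0167, since the SAP gives no figure. No gain in precision from covariates is assumed.

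**Reproducing the plan's figure.** n = 2 × (2.393 + 0.842)² / 0.33² = 192.2, so 193 per arm by the normal formula. The two-sample t-test solution is 193.6, so 194, as stated. A one-sided test would give 162. The 0.0167 is therefore a two-sided level.

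**Interval width.** The critical values are 2.393 for ALPHA=0.0167 and 1.960 for 0.05. Their ratio is 2.393 / 1.960 = 1.22, so the limits from the code are 22% wider at any SD or sample size.

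**Where the two intervals disagree about zero.** SE = 16 × √(2/n). The lower edge of the band is 1.960 × SE and the upper edge is 2.393 × SE.

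| n per arm | SE | Lower edge | Upper edge |
|---|---|---|---|
| 194 | 1.625 | 3.18 | 3.89 |
| 203 | 1.588 | 3.11 | 3.80 |

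An observed difference inside the band has a 95% interval that excludes zero and a 98.33% interval that includes it. The band is about 0.7 points wide.

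**Chance of landing in the band.** For a true difference d, this is Φ(2.393 − d/SE) − Φ(1.960 − d/SE), plus the matching lower tail, which matters only near d = 0.

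- d = 0: 0.05 − 0.0167 = 3.3%.
- d = 5.3, n = 194: d/SE = 3.262. The chance that the interval excludes zero on the favourable side is 90.4% at 0.05 and 80.8% at 0.0167. The difference is 9.6%.
- d = 5.3, n = 203: d/SE = 3.337. The corresponding figures are 91.6% and 82.7%, and the difference is 8.8% before rounding.
- Maximum: at the middle of the band, d/SE = (1.960 + 2.393)/2 = 2.177, which is d of about 3.5 points. The chance is Φ(0.217) − Φ(−0.217) = 17.2%.

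**What the ALPHA option does.** In LSMEANS it sets the coverage of the printed limits. The p-values do not depend on it.

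**The case against.** The strongest reply is that the text already settles the rule. Section 11.6 is the section on multiplicity, it is explicit about secondary hypotheses, and section 11.1 limits 98.3% intervals to H1-H3. LSMEANS prints every pair, including Arm 3 vs 1, which is no hypothesis in the SAP, so printing a pair does not make a decision rule for it. The wording in section 11.2.1 reads naturally as the same model and covariates. Section 8.3 keeps the arms masked until the analyses are completed, which limits the scope for choosing a level to suit a result.

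Most of this stands, and it rules out two stronger readings. A reader might infer that the SAP sets two significance levels for H4 and H5. It does not: ALPHA= leaves the p-values alone, and section 11.6 is the only explicit multiplicity rule. A reader might also extend the conflict to the other secondary outcomes. The documents do not support that, because the only model is for KOOS Pain change and the 98.3% label in Table 2 sits only in the KOOS Pain row. For those outcomes the level is unstated, not contradicted.

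The reply does not remove the mismatch in the intervals. The program's heading claims the secondary analyses, and the one statement that yields H4 and H5 gives them limits that the text does not.

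**Conclusion.** The concern holds as a minor mismatch between code and text, confined to the confidence intervals for H4 and H5 on KOOS Pain. Run as written, the program gives these two contrasts limits 22% wider than the unadjusted rule implies. It matters to the reading only when the estimate falls in a band about 0.7 points wide. The 17% maximum should not be taken as typical: it applies only if the true difference is near 3.5 points, and section 8.5 does not say that the 10-12 points between Arms 1 and 4 divide equally among the components.

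The result rests on SD 16, 194 to 203 per arm, no covariate gain, and a two-sided 0.05 inferred from the absence of adjustment. A smaller residual SD would narrow the band in points but would not change the 22% ratio. H1-H3 and the primary conclusions are unaffected.

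**What to change.** - In section 13.3, replace the blanket LSMEANS option with ESTIMATE statements for H1-H3 at ALPHA=0.0167. Add ESTIMATE or contrast statements for H4 and H5, with ALPHA=0.05 so that they give 95% intervals.
- In sections 11.2.1 and 11.6, state the two-sided test level and confidence level for H4 and H5, and say that these results are not controlled for multiplicity. The same sentence can name the level for the other secondary outcomes.
- Print the confidence level in the appendix table for H4 and H5 and in the remaining rows of Table 2.

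The cost is a sentence or two of text, a few lines of code and some table labels. Data, sample size and the primary analysis do not change. It is best done before the arms are unmasked.
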